**Table 8.8-1. Extended study exam schedule**

	Pre-op	Intra-op	Pre-discharge	Month						
				1	6	12	24	36	48	60
CT Scan 	X			X 						
Angiography	X 	X								
Blood tests 	X		X	X	X	X	X	X	X	X
Clinical Exam	X		X	X	X	X	X	X	X	X

 Selective angiography may be requested to provide more focused imaging if potential device integrity issues are identified, but are unable to be confirmed, using CT.

 In patients experiencing renal failure during follow-up, selective angiography (preferred) or duplex ultrasound may be used in conjunction with non-contrast CT.

 It is recommended that all previously enrolled patients who received the ConnectSX™ undergo CT follow-up to assess stent integrity every six months unless the stent has been relined to treat an observed or threatened Type III endoleak.

 Pre-procedure angiography may be requested at discretion of film reviewer/proctor.

 Blood tests include creatinine.

## 8.9. Criteria and Procedures for Extended Study Termination

A patient's follow-up in the extended study will end after:

- 1) Failure to deploy the device + 30 days
- 2) Conversion to open surgical technique + 30 days
- 3) Patient withdrawal
- 4) Patient death

- 5) Closure of the investigation
- 6) Completion of all scheduled clinical and imaging visits, up to 5 year follow-up

## 8.10. Statistical Considerations

### 8.10.1 Sample Size

Bayesian simulation studies were performed to determine the sample size required to test the study hypotheses with sufficient statistical power (in the frequentist context).

For the power calculation of the primary hypothesis, the true patency rate of the IIA following treatment with the Branch Graft was assumed to be 83% based on the literature. With a performance goal of 55% for freedom from patency-related intervention (derived as described in section 4.3.1), the simulation study indicates that a maximum sample size of 25 patients will provide a power of approximately 88.5%, at a type I error rate of 2.5%.

For the secondary safety hypothesis, the true rate of freedom from 30-day morbidity was assumed to be 72.5%, which was derived from patients with patent internal iliac arteries in the Zenith® AAA Endovascular Graft Clinical Study who were free from 30-day morbidity (i.e., free from all 31 events in the Zenith® AAA Endovascular Graft Clinical Study morbidity index and hip/thigh/buttock claudication). With a performance goal of 46% for freedom from 30-day morbidity (derived as described in section 4.3.2), the simulation study indicates that a maximum sample size of 29 patients will provide a power of 85.8%, at a type I error rate of 2.5%.

---


Cook intends to enroll 40 patients with the Zenith® Branch Endovascular Graft-Iliac Bifurcation and Atrium iCAST™ covered stent, allowing for those who may withdraw or be lost to follow-up, in the study at up to 30 institutions.

### **8.10.2 General Statistical Analyses**

Statistical analysis will be performed only on the cohort of patients treated with the Zenith® Branch Endovascular Graft-Iliac Bifurcation in combination with the Atrium iCAST™ covered stent as part of the extended study. SAS® for Windows® (release 9.3 or higher) or other widely accepted statistical software will be used to perform the analysis. Continuous variables will be reported as means and standard deviations unless otherwise noted. Categorical variables will be reported as percent. Techniques such as logistic regression, Kaplan-Meier, or Cox Proportional Hazards may be used for additional analysis.

### **8.10.3 Missing Data**

The primary and secondary hypotheses will be assessed using the intent-to-treat patient population. Any patient that is considered missing for this endpoint analysis will first be examined to determine if best-available data can be used to assess the endpoint. Previous clinical trial experience suggests that some portion of the imaging data may not meet the criteria for accurate review by the core laboratory; however, it is recognized that the investigator uses this information to provide the best possible care for the patient. Therefore, it is reasonable to substitute any missing core laboratory measurements with the corresponding measurements made by the investigator or institutional staff. Otherwise, missing responses will be imputed from the empirical distribution of responses. Additional analyses may also be performed to address missing data, including tipping point analysis.

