##### **4.1. Primary Objectives**

Primary Endpoint: The primary assessment will be based on 6-month freedom from patency-related intervention since the Zenith® Branch Endovascular Graft-Iliac Bifurcation is intended to maintain blood flow to the internal iliac artery and minimize the risk of associated clinical symptoms with the need for reintervention.

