## **8.7. Registration/Point of Enrollment**

Point of enrollment will be based on the intent-to-treat population, and is defined to include any patient for which the treatment procedure is initiated. More specifically, once the delivery system of the study device (Zenith® Branch Endovascular Graft-Iliac Bifurcation) has been inserted under the patient's skin, this patient would be included in the intent-to-treat population. Primary statistical analyses will be based on this set of patients.

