## **10.0. Deviations from the Clinical Investigation**

Deviations or non-compliances will be recorded together with an explanation. Deviations shall be reported to the Sponsor, regulatory authorities, and local IRB/ethics committee as required.

When available, the reasons for withdrawal and discontinuation of any patient from the investigation shall be recorded. If such discontinuation is because of problems with safety or lack of effectiveness, that patient shall still be followed-up in the investigation, if possible.

If appropriate, corrective and preventive actions will be discussed by the sponsor, investigator, and/or IRB to determine a suitable course of action.

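### Section 8.9 stops follow-up 30 days after failed deployment or open conversion, so the 6-month primary endpoint goes unobserved by design for some intent-to-treat patients

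*Protocol*

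**What the plan says.** **Endpoint.** Protocol 4.1: "The primary assessment will be based on 6-month freedom from patency-related intervention". Under Patency-Related Intervention, Attachment B includes secondary interventions for symptoms after a technical failure that occluded the internal iliac artery at the implant procedure.

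**Analysis set.** Once the delivery system is under the skin, 8.7 states that "this patient would be included in the intent-to-treat population", and then: "Primary statistical analyses will be based on this set of patients". Section 8.10.3 agrees: "The primary and secondary hypotheses will be assessed using the intent-to-treat patient population".

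**End of follow-up.** Section 8.9 lists "Failure to deploy the device + 30 days" and "Conversion to open surgical technique + 30 days" among the points at which a patient's follow-up ends.

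**Possible mitigation.** For discontinuation because of safety problems or lack of effectiveness, 10.0 says "that patient shall still be followed-up in the investigation, if possible".

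**Missing data.** Section 8.10.3 looks first for best-available data and allows site measurements to replace missing core laboratory ones. Then: "Otherwise, missing responses will be imputed from the empirical distribution of responses". Tipping point analysis is named as something that may be added.

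**The concern.** The protocol defines an endpoint event that can follow a technical failure, and keeps such patients in the primary analysis. It then stops observing failed deployments about 150 days before the endpoint is read.

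This is not ordinary dropout, because the plan itself creates the gap. Nor is it random, because it is tied to procedural failure. The fallback imputation makes no distinction by reason for missingness, so an unresolved failed deployment would receive a response drawn mainly from patients who remained in follow-up. No SAP can recover a 6-month status that was never collected.

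At stake is how far the primary result describes all patients in whom the procedure was started. With 40 patients, each unresolved exit can move the observed rate by up to 1/40 = 2.5 percentage points. That matters only for a result near the pass threshold.

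**Working it through.** **1. Size of the gap.** The 6-month visit is at day 180 (8.8). A deployment failure on day 0 ends follow-up at day 30, leaving 180 − 30 = 150 days unobserved. A conversion on day d ends follow-up at d + 30, so any conversion before about day 150 leaves a gap. The 30-day safety endpoint is largely unaffected.

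**2. The plan's own figure.** The protocol text at hand does not state the prior, so a flat Beta(1,1) is assumed. The pass rule is that the 2.5th percentile of Beta(1 + x, 1 + n − x) exceeds 0.55.
- At n = 25 this needs x ≥ 19. Power is P(Bin(25, 0.83) ≥ 19) = 88.15%, against about 88.5% in 8.10.1. Type I error is 2.58%, close to the stated 2.5%. The assumed rule therefore reproduces the plan.
- At n = 40 it needs x ≥ 29, so up to 11 failures are tolerated. Beta(0.5, 0.5) gives the same cut-off. With complete data the false-pass rate is P(Bin(40, 0.55) ≥ 29) = 1.79%, and the pass probability at 83% is 96.99%.

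**3. Model for unresolved exits.** The protocol gives neither the number of exits nor their outcomes, so both are assumptions shown as a range.
- f is the share of patients who exit under these two items of 8.9 and stay unresolved. q is the event-free share among them.
- The overall true rate is π. The rate in the others is then (π − f·q)/(1 − f). For example, at π = 0.55, f = 0.10 and q = 1 it is (0.55 − 0.10)/0.90 = 0.50. At q = 0.55 it is (0.55 − 0.055)/0.90 = 0.55.
- M ~ Bin(40, f) exits. X ~ Bin(40 − M, rate in the others). Imputed successes ~ Bin(M, X/(40 − M)), drawn once. The trial passes if X plus the imputed successes is at least 29.

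**4. Results (exact sums).**

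| Unresolved exits f | 2.5% | 5% | 10% | 15% |
|---|---|---|---|---|
| Average number of 40 | 1 | 2 | 4 | 6 |
| False pass, π = 55%, q = 1 | 1.4% | 1.1% | 0.7% | 0.4% |
| False pass, π = 55%, q = 0.55 | 2.0% | 2.3% | 2.8% | 3.5% |
| Pass, π = 83%, q = 1 | 96.0% | 94.9% | 92.0% | 88.1% |
| Pass, π = 83%, q = 0.55 | 97.5% | 98.0% | 98.7% | 99.3% |

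For f from 5% to 15%, the rule leaves the false-pass rate at its complete-data value when q is about 0.70 to 0.71. Above that it is conservative.

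At q = 0.55 the estimated rate is not shifted, since the others also have a rate of 55%. The rise above 1.8% there comes from the random draw being counted as real data. If the observed rate is filled in instead, the q = 0.55 figures are 1.4%, 1.6% and 1.9% at f = 5%, 10% and 15%.

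**The case against.** **The protocol already handles part of this.** Events up to 30 days after the failure or conversion are observed, best-available data come before any imputation, and 10.0 asks for follow-up to continue where feasible. This stands in part: imputation applies only to the unresolved remainder. But 10.0 covers only discontinuation for safety or lack of effectiveness and does not say how it fits with 8.9. Best-available data also cannot show an event that nobody was asked to record.

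**Imputation detail belongs in the SAP.** This largely stands. The number of draws and any conditioning on reason for missingness may properly be fixed there. The core defect is in 8.9, not in the imputation sentence.

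**A stronger reading is tempting: that the plan favours the device.** If every unresolved exit were a failure, the same model would give false-pass rates of 4.9%, 11.5% and 23.0% at 5%, 10% and 15% exits. The documents do not support that scenario. Failed deployment or conversion is not itself an endpoint event, because the definition requires a secondary intervention for symptoms. Section 4.3.1 puts symptoms after sacrifice of the artery at about 45%, with no good endovascular remedy. If that figure carried over to these exits, which is an assumption, at least 55% would be event-free.

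**A reader might also infer that the missingness is device-related.** The protocol does not say so. Section 8.13 has the events committee separate pre-existing, procedure-related, technique-related and device-related causes. Procedural failure is as far as the text goes.

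**Conclusion.** The inconsistency is real. Section 8.9 stops observation that the 6-month intent-to-treat endpoint needs, and neither 10.0 nor the best-available-data step secures it.

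The direction of any bias is unknown. Over exit shares of 2.5% to 15%, the false-pass rate at the 55% goal is about 0.4% to 1.4% if all unresolved exits are event-free and 2.0% to 3.5% if 55% are, against 1.8% with complete data. Higher values need more than 45% of exits to have events, which nothing in the protocol indicates. At the planned 83% the conclusion would rarely change. With one or two exits on average, the pass probability stays within about 2 points of 97.0%. The largest shift in the table, to 88.1%, goes against the device and needs 15% unresolved exits, all event-free.

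These figures rest on 40 patients, a flat prior, a single imputation draw and assumed exit shares. Severity is minor to moderate: the effect is probably small, but the gap is avoidable and its size could not be judged afterwards.

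**What to change.** 1. Reconcile 8.9 with 10.0 and the 6-month endpoint. Record 6-month patency-related intervention status, where obtainable, for every intent-to-treat patient, including failed deployments and conversions. Use it in the primary analysis under the existing definition.
2. In 8.10.3, keep the stated imputation in the primary test for whatever is still missing. Make the tipping point analysis mandatory as a supportive analysis, and include the bound that counts unresolved exits as failures.

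**Cost.** Wording in 8.9, 10.0 and 8.10.3, a status check for the few patients concerned, and one supportive analysis. The endpoint, 55% goal, sample size and primary test stay unchanged.

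**Downside.** The worst-case rate falls by up to 2.5 points per unresolved exit. With the others at 83%, the bound alone would pass with probability P(Bin(40, 0.83 × (1 − f)) ≥ 29) = 88%, 70% and 47% at f = 5%, 10% and 15%. It should therefore not replace the primary test.

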### 4.3. Specific Hypothesis to be Accepted or Rejected by Statistical Data

#### 4.3.1. Primary Hypothesis

The primary hypothesis will assess the rate of freedom from patency-related intervention evaluated at 6 months and will be based on results from the cohort of patients treated with the Zenith® Branch Endovascular Graft-Iliac Bifurcation in combination with the Atrium iCAST™ covered stent as part of the extended study. The analysis requires that, using a Bayesian beta-binomial model, a specified performance goal described in the following sentences be met. The Zenith® Branch Endovascular Graft-Iliac Bifurcation (Branch Graft) is intended to preserve flow to the internal iliac artery (IIA), providing an alternative treatment option for patients who would otherwise require sacrifice of the IIA through coil embolization and stent-graft coverage of the IIA as part of endovascular aneurysm repair of aortoiliac or iliac aneurysms. In order to provide the most meaningful labeling for clinical decision making on whether to sacrifice or preserve the IIA, it was determined appropriate to base the performance goal for the Branch Graft on outcomes associated with sacrificing the IIA, which represents the only endovascular treatment option currently available for the intended patient population. Specifically, unilateral coil embolization and stent-graft coverage of the IIA results in pelvic ischemic symptoms/complications in approximately 45% of patients with no good option for alleviating the symptoms through endovascular means. Based on this, a performance goal of 55% for freedom from patency-related intervention was established.

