- Secondary intervention to treat a > 60% stenosis of the internal iliac artery (as identified through CT, angiography, or duplex ultrasound and confirmed by core laboratory) associated with clinical symptoms. Of note, this not only includes patients with internal iliac artery stenosis following successful placement of the Zenith® Branch Endovascular Graft-Iliac Bifurcation and covered bridging stent, but also any cases of technical failure resulting in occlusion of the internal iliac

artery during the initial implant procedure that require secondary intervention for associated clinical symptoms.

*Renal Failure:* Acute or progressive renal insufficiency leading to the need for dialysis or hemofiltration.

*Renal Insufficiency:* A rise in serum creatinine of more than 30% above the pre-procedure level, resulting in a serum creatinine level  $> 2.0$  mg/dl that does not spontaneously resolve (does not include those patients with a pre-procedure serum creatinine  $> 2.0$  mg/dl).

*Serious Adverse Event:* An adverse event that led to death, led to a serious deterioration in the health of the subject that resulted in a life-threatening illness or injury, resulted in a permanent impairment of a body structure or a body function, required in-patient hospitalization or prolongation of existing hospitalization, resulted in medical or surgical intervention to prevent permanent impairment to body structure or a body function, led to fetal distress, fetal death, a congenital abnormality or birth defect.

*Stent/attachment system fracture/break:* Fracture or breakage of any portion of the Zenith® Branch Endovascular Graft-Iliac Bifurcation or covered bridging stent or attachment system including metallic fracture or breakage of any suture material used to construct the stent or secure the stent or attachment system to the graft material as determined by the core laboratory and confirmed by CEC.

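### Filling missing responses from the empirical distribution adds no information to either test and can distort the posterior; test on observed responses and commit to a tipping-point analysis

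*Protocol*

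**What the plan says.** Protocol section 8.10.3 sets the population: "The primary and secondary hypotheses will be assessed using the intent-to-treat patient population". A missing response is first settled from best-available data, including investigator readings in place of core-laboratory ones. For what remains, "Otherwise, missing responses will be imputed from the empirical distribution of responses". Sensitivity work is optional: "Additional analyses may also be performed to address missing data, including tipping point analysis".

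Section 4.3.1 requires that, "using a Bayesian beta-binomial model, a specified performance goal described in the following sentences be met". The primary null is rejected if the 2.5th percentile of the posterior exceeds 55%. Section 4.3.2 applies the same percentile rule to 30-day morbidity with a goal of 46%. It speaks only of a Bayesian posterior, so the beta-binomial model is named for the primary test and inferred for the secondary.

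Three further places bear on who has a 6-month response. Section 8.7 puts every patient in whom the delivery system was inserted into the intent-to-treat set and adds: "Primary statistical analyses will be based on this set of patients". Section 8.9 ends follow-up after "Failure to deploy the device + 30 days" and after "Conversion to open surgical technique + 30 days". Section 8.10.2 restricts the analysis to patients treated with the graft together with the iCAST stent. In Attachment B, patency-related intervention covers stenosis after successful placement, "but also any cases of technical failure resulting in occlusion of the internal iliac" artery that need secondary intervention for symptoms.

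**The concern.** A value drawn from the observed responses repeats what those responses already say. If it enters the beta-binomial model as one more patient, the posterior is narrower than the data justify and its 2.5th percentile moves. A borderline result then depends on the random seed. Both confirmatory decisions rest on that percentile, at a nominal type I error of 2.5% (section 8.10.1).

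The rule also assumes that missing patients resemble observed ones. That is least credible for patients whose follow-up stops 30 days after failed deployment or conversion, who can lack a 6-month response. The one analysis named that would test the assumption need not be done.

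**Working it through.** **Inputs.** From the protocol: goals of 55% and 46%; assumed true rates of 83% and 72.5%; required sizes of 25 and 29; 40 to be enrolled. My assumptions: a flat Beta(1,1) prior (none is stated), responses missing at random, and 4, 8 or 11 of 40 still missing (no drop-out rate is stated, so this is a range and not a forecast).

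**Cut-off.** cut(n) is the smallest x for which the 2.5% quantile of Beta(1+x, 1+n−x) exceeds the goal.

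**The plan's own figures.** Primary, n=25: cut-off 19, power P(Bin(25, 0.83) ≥ 19) = 88.2%, against about 88.5% stated. Secondary, n=29: cut-off 19, power P(Bin(29, 0.725) ≥ 19) = 85.3%, against 85.8% stated. The stated powers are reproduced. Exact type I error is 2.58% and 2.72%, so the stated 2.5% is nominal. At n=40 the cut-offs are 29 (primary) and 25 (secondary).

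**Observed responses only.** Error = P(Bin(n_obs, goal) ≥ cut(n_obs)).

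**Single draw counted as a patient.** Error = Σ over x of Bin(x; n_obs, goal) × P(Bin(40−n_obs, x/n_obs) ≥ cut(40)−x).

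| Missing of 40 | Primary, single draw | Primary, observed only | Secondary, single draw | Secondary, observed only |
|---|---|---|---|---|
| 2 | 2.3% | 3.2% | 3.3% | 2.5% |
| 4 | 2.8% | 2.6% | 4.0% | 2.3% |
| 8 | 4.1% | 1.6% | 5.5% | 2.0% |
| 11 | 5.2% | 1.7% | 6.7% | 2.7% |

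With 1 missing the primary figures are 2.0% (single draw) and 2.4% (observed only). So at 1 to 2 missing the primary effect is reversed, and up to 4 missing it is no larger than the jumps caused by an integer cut-off.

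**Dependence on the seed (single draw, primary).**
- 23/32 has a 2.5th percentile of 0.545 and misses on observed data. With 8 drawn values it passes with probability P(Bin(8, 23/32) ≥ 6) = 60%.
- 26/36 has 0.559 and passes. With 4 drawn values it fails with probability 31%.
- At 8 missing and a true rate at the goal, two seeds on the same data disagree in 3.3% of trials (primary) and 4.4% (secondary).

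**Averaged draws.** The test passes if the mean over draws of P(rate > goal) exceeds 0.975. For 1 to 15 missing, the cut-off equals the observed-only one except at 5, 8, 11 and 14 missing (primary) and 3, 10 and 12 (secondary), where it is one success laxer. It is never stricter. At 8 missing the primary error is then 3.9%, against 1.6% on observed responses.

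**Why averaging does not fully cure it.** The draws treat x/n_obs as the known rate. At 23/32 the posterior SD is 0.077 on observed responses, 0.075 with averaged empirical draws, and 0.069 when six of eight drawn successes count as patients (29/40). If draws instead come from the posterior predictive distribution and are averaged, the result is Beta(a+x, b+n_obs−x), the observed-only posterior; numerically the two differ by less than 1e-14 for all x, 1 to 15 missing and both goals.

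**Informative missingness.** Let the overall rate equal the goal and all missing patients be failures, so that the observed rate is 40×goal/(40−missing). With 4 missing, error is 11.4% observed-only and 11.5% single draw (primary), and 8.5% and 12.2% (secondary). With 2 missing, the primary gives 6.8% and 4.9%. Neither method protects against this.

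**The case against.** The strongest reply is that the larger errors and the seed dependence need one draw per patient counted as observed, which the protocol does not state. The number of draws and how they are combined is normally left to the SAP, which is not shown. Averaging is natural in a Bayesian analysis and gives the observed-only cut-off at 11 of 15 missing counts (primary) and 12 of 15 (secondary). This stands as a limit on the size of the problem. It does not rescue the rule: averaged or not, the draws can only match the observed-data posterior or distort it.

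Eight or 11 missing of 40 is also not supported by the text, particularly at 30 days and after the best-available-data step. That stands too; the figures show direction and scale only.

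Observed-only testing is not uniformly better. It has the higher primary error at 1 to 2 missing and makes the same missing-at-random assumption. This is why the tipping-point analysis belongs in the fix.

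Two stronger readings are tempting. A reader might infer that the rule steadily favours passing, or loses passes at low missingness and creates false ones at high. With the true rate at the goal, losses exceed gains only at 1 to 2 missing. At a true 83% the balance alternates (8 missing: 1.2% lost, 3.3% gained; 10 missing: 2.6% lost, 1.5% gained), and a gained pass there is not false. A reader might also infer that failed deployments will be imputed mostly as successes. Section 8.7 would bring them into the test, but section 8.10.2 may leave them out, and best-available data may settle their status. The documents do not decide this.

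**Conclusion.** The concern holds in limited form. Section 8.10.3 fixes a method for both confirmatory tests that adds no information and can distort the decision. If each draw counts as a patient, type I error exceeds the observed-only figure by 2.5 and 3.5 percentage points in the primary test at 8 and 11 missing (4.1−1.6; 5.2−1.7), and by 1.7, 3.5 and 4.0 points in the secondary at 4, 8 and 11 (4.0−2.3; 5.5−2.0; 6.7−2.7). If draws are averaged, the effect is at most one success in the cut-off. All of this assumes 40 patients, a flat prior and responses missing at random; the missing counts are illustrative.

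The firmer points do not depend on the number of draws: the imputation cannot address informative missingness, the tipping-point analysis is not promised, and sections 8.7, 8.9 and 8.10.2 leave open how patients with follow-up cut short by rule count at 6 months. The sponsor should correct this, but it does not show that the trial's conclusion would be wrong.

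**What to change.** 1. After the best-available-data step, base both tests on Beta(a+x, b+n_obs−x) from the observed responses. By the identity shown above, this equals averaging over posterior-predictive draws for all 40, so the intent-to-treat set is kept.
2. Commit to a tipping-point analysis over all intent-to-treat patients for both tests. For example, 26/36 passes the primary test, but with all 40 counted it needs 29/40, that is, 3 of the 4 missing as successes.
3. Reconcile sections 8.7, 8.9 and 8.10.2, and state in advance how patients whose follow-up ends early by rule count in the primary test.

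The cost is two or three sentences, no extra patients, and usually a little power. At 32 observed, power is 91.9% against 94.0% with single draws (primary) and 85.7% against 90.3% (secondary). At 36 observed the primary gains (96.7% against 95.6%) and the secondary loses (90.8% against 92.2%). Over 25 to 40 observed, the lowest primary power is 86.0%, at 26. Secondary power falls below 80% at 28 observed (78.1%) and 25 observed (77.1%), both short of the planned 29. Because the cut-off is an integer, type I error still varies over that range: 1.5% to 3.4% (primary) and 1.6% to 3.7% (secondary).
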